#### *8.2.6 Duration of the study*

Participants will participate in the study for approximately 9 weeks: participants will have approximately 1 week to complete at-home baseline assessments (3-day food log and questionnaires), and then the study lasts 8 weeks.

### 8.2.7 Schedule of assessments

Baseline assessments will optimally be collected before the first infusion of chemotherapy, though assessments will not delay chemotherapy. Baseline assessments after chemotherapy is initiated is permissible as long as the patient has at least 6 more weeks of chemotherapy. 4-Week assessments will occur approximately during week 4 (during week 3-5); 8-week assessments will occur approximately during week 8, the last week of the intervention (week 7-9). However, this may be adjusted to accommodate factors such as the participant or researcher's schedule. Because of the immediate and transient effects that chemotherapy has on fatigue, we will aim to have assessments at least 3 days after an infusion. Optimally, the post-intervention assessments will occur during the last week of the intervention, while the participant is still on the diet, so that we can probe metabolic markers that may change quickly after cessation of the diet. **Table 3** describes two common chemotherapy regimens, but others exist and we will work around clinic activities to collect assessments.

Study Week	0	1	2	3	4	5	6	7	8
Study activities	Consent, Baseline assessments				4-week assessments				8-week assessments
Infusion number (for patients on biweekly regimens)		1		2		3		4	
Infusion number (for patients on weekly regimens)		1	2	3	4	5	6	7	8
Infusion number (for patients on an every 4-week regimen)		1				2			
Infusion number (for patients on an every 3-week regimen)		1			2			3	

**Table 3.** Schedule of chemotherapy infusions and study activities for two example chemotherapy regimens.

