## 2. Background and rationale

### 2.1 Background

#### 2.1.1 Cancer-related fatigue in the cancer experience

Cancer-related fatigue affects up to 90+% of patients undergoing chemotherapy, depending on the type of cancer and treatment as well as the measure used to evaluate fatigue. It is not relieved by sleep or rest, and its severity can greatly hinder the ability to perform activities of daily living and decrease quality of life. The mechanisms behind the etiology and pathophysiology of cancer-related fatigue seem to be related in part to inflammation, but largely are not understood, thereby thwarting the development of effective preventative strategies and treatments. Cancer-related fatigue is one of the most debilitating symptoms in types of cancer that are typically treated outpatient with high cure rates, such as breast and bladder cancer. Fatigue trajectories tend to increase on average throughout the course of treatment with local maxima several days after each infusion cycle, and then recover after treatment, though fatigue often does not return to baseline.

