#### *4.4.2 Aim 2: Patient-reported fatigue measures*

Aim 2 of our study is to assess the effects of the Mediterranean Diet on cancer-related fatigue, as assessed using the FACIT-F. Patients will complete this instrument at baseline, 4 weeks, and 8 weeks.

1. Functional Assessment of Chronic Illness-Fatigue (FACIT-F) questionnaire: The FACIT-F is a 40-item, validated, commonly used measure of fatigue that is comprised of 5 subscales: physical well-being, social well-being, emotional well-being, functional well-being, and fatigue-specific well-being. It captures fatigue in these categories over the last 7 days. The 13-item FACIT-F fatigue subscale will be used as the primary aim.

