## 17. Data analysis plan

### 17.1 Sample size determination

This is a two-arm randomized controlled trial that will assess feasibility of delivering a Mediterranean Diet intervention to patients undergoing chemotherapy, as well as the preliminary efficacy of a Mediterranean Diet intervention vs. usual care on the prevention of cancer-related fatigue. Our sample size is based on our fatigue outcome as measured using the FACIT-F fatigue subscale, which is a 13-item scale with responses that range from 0-4; the FACIT-F subscale score ranges from 0-52 and a higher score indicates greater wellbeing and less fatigue. The minimal clinically important difference for the FACIT-F is 3 points.

We plan to recruit a total of 42 participants and randomize them in a 2:1 ratio, intervention: control (28:14) using computer-generated block randomization with blocks of 3 or 6. Patients will be stratified based on how frequently their chemotherapy is planned to be administered. One strata will include patients who plan to receive weekly, biweekly (Q2w), or every 4-week (Q4w) regimens, and the other strata will include those on other regimens (e.g., Q3w). Thus, those in the first strata will complete 4-week and 8-week assessments for our study at the end of a chemotherapy cycle, while those in the second strata will be completing assessments in the middle of their cycle. (If there are

**Fig. 3.** Effect size vs. sample size at 70% and 80% power with 33 participants on the study.

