dose delays or changes to the chemotherapy schedule, we will still collect assessments at the originally planned time.) We estimate attrition between approximately 20 and 25%, thus we estimate to retain 33 (22:11) evaluable patients. This sample size is appropriate for small randomized pilot studies and it will allow us to obtain preliminary estimates of descriptive statistics [mean, standard deviation (SD), and confidence intervals (CI)]. The primary endpoint is the change in fatigue as measured by FACIT-F from baseline (T1) to 4 weeks (T2). Assuming a correlation of 0.50 between T1 and T2 FACIT-F measurements, a total sample size of n=33 will provide 80% power at the 0.15 two-sided significance level to detect an effect size (ES, standardized mean between-group difference) of 0.75 of the intervention effect on change in T2-T1 FACIT-F using analysis of covariance (ANCOVA) with T1 FACIT-F as a covariate (**Fig. 3**). The estimates of T1-T2 correlation and attrition rate are based on our prior studies.

Feasibility is often determined for nutrition interventions among 10-15 participants (e.g.,); pilot preliminary efficacy studies usually recruit 20-30 (e.g.,). **Table 6** below shows prior studies that are similar to this one, including their sample size.

Study	n	Population	Intervention	Outcome	Results
Zick et al. (2017) 	30	breast cancer survivors	Fatigue reduction diet vs. General Health Curriculum (time and attention control) for 3 months	Brief Fatigue Inventory	From baseline to 3-months, fatigue improved by 44±39% in diet group compared to 8±34% in the control group (p=0.01)
Skouroliakou et al. (2018) 	70	breast cancer survivors	Mediterranean Diet for 6 months vs. handout	serum antioxidant capacity and body composition	The dietary intervention based on Mediterranean Diet improved serum antioxidant capacity, body composition, and glycemic profile.
McMillan et al. (2011) 	27	healthy women in their 20's	Mediterranean Diet vs. control for 10 days	Profile of Mood States	A group × time interaction demonstrated that the Mediterranean Diet reduced fatigue (p=0.16) and improved vigor (p<0.01).

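### The aim of assessing at least 3 days after an infusion does not fit FACIT-F's 7-day recall, so the 4-week fatigue scores mix cycle positions by regimen

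*Combined protocol and SAP*

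**What the plan says.** Section 8.2.7 gives the reason for the spacing aim: "Because of the immediate and transient effects that chemotherapy has on fatigue". The aim itself is that "we will aim to have assessments at least 3 days after an infusion". The same section sets the window: "4-Week assessments will occur approximately during week 4 (during week 3-5"), with week 7-9 for the 8-week visit. Both may be adjusted for the participant's or researcher's schedule. Baseline is preferably taken before the first infusion, but may be taken later.

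Section 17.1 defines the fatigue endpoint: "The primary endpoint is the change in fatigue as measured by FACIT-F from baseline (T1) to 4 weeks (T2"). Section 4.4.2 says of FACIT-F: "It captures fatigue in these categories over the last 7 days". Section 2.1.1 describes the course of fatigue: "Fatigue trajectories tend to increase on average throughout the course of treatment with local maxima several days after each infusion cycle".

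Randomisation is stratified by regimen frequency: weekly, every-2-week and every-4-week in one stratum, all others in the second. Section 17.1 expects that "those in the first strata will complete 4-week and 8-week assessments for our study at the end of a chemotherapy cycle", and that the second stratum is assessed mid-cycle. It also keeps assessments on their planned dates if doses are delayed. The 4-week ANCOVA in section 17.4.2 contains arm and baseline FACIT-F. Neither the stratum nor time since infusion is named there or in the mixed model.

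**The concern.** The spacing aim has a stated purpose, and for the endpoint that matters most it cannot serve it. A 3-day gap takes the infusion day out of a question about the last 24 hours. It does not take it out of a question about the last 7 days. If fatigue peaks several days after an infusion, a form completed just after the 3-day minimum may fall near that peak.

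What then decides whether post-infusion days enter the score is the regimen and the date chosen inside a three-week window. Two patients with the same underlying fatigue course can give different 4-week scores because of when they filled in the form. The estimates at stake are the 4-week contrast, with about 11 evaluable controls, and the T1-T3 means, SDs and change scores, which section 17.4.2 intends for planning a future randomised trial.

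**Working it through.** **The plan's own figure.** Inputs from section 17.1: 22 and 11 evaluable, effect size 0.75, T1-T2 correlation 0.50, two-sided alpha 0.15.
- Residual SD in SD units: √(1 − 0.50²) = 0.866.
- Standard error factor: √(1/11 + 1/22) = 0.369.
- Noncentrality: 0.75 / (0.866 × 0.369) = 2.35.
- Power: 0.817 (normal) or 0.806 (noncentral t, 30 df). The stated 80% reproduces.

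**Day count.** Assumptions: each infusion falls on the first day of its Table 3 week, day 0 is infusion 1, and week k runs from day 7(k − 1) to day 7k − 1. The recall is the completion day and the six days before it, so an infusion is inside the recall when days since infusion are 6 or fewer.

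Nominal week 4 (days 21-27), keeping only days at least 3 after an infusion:

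| Regimen | Last infusion | Compliant days | Days since infusion | Infusion in recall |
|---|---|---|---|---|
| Weekly | day 21 | 24-27 | 3-6 | 4 of 4 |
| Every 3 weeks | day 21 | 24-27 | 3-6 | 4 of 4 |
| Every 2 weeks | day 14 | 21-27 | 7-13 | 0 of 7 |
| Every 4 weeks | day 0 | 21-27 | 21-27 | 0 of 7 |

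If the recall is instead read as the seven days before completion, only the every-2-week row changes, to 1 of 7 (day 21).

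Over the full window (days 14-34), the compliant days with an infusion in the recall are: weekly 12 of 12, every-2-week 8 of 15 (53%), every-3-week 4 of 18 (22%), every-4-week 4 of 18 (22%).

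**Strata.** Weekly and every-3-week patients look alike on this measure but sit in different strata. Weekly and every-4-week patients share a stratum but differ from 3-6 to 21-27 days.

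**Week 4 against week 8.** In nominal week 8 (days 49-55) the last every-3-week infusion is on day 42, so those patients are 7-13 days out, against 3-6 in week 4. The other three regimens keep the same position.

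**The peak.** The documents give no exact day. If days 3-5 are assumed, a form on day d recalls days d − 6 to d and clears the peak only when d − 6 > 5, that is, at 12 days or more. On that assumption the every-2-week recall still touches a peak day on 5 of the 7 week-4 days.

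**Illustrative size (assumptions, not in the documents).** Let T2 variance grow by a fraction e, so the residual SD is √(1 + e − 0.25). Power is 0.806 at e = 0, 0.766 at 10%, 0.711 at 25% and 0.636 at 50%. To place e: if half the patients score 3 to 6 points lower (one to two times the 3-point MCID), the added variance is 0.25 × 3² = 2.25 to 0.25 × 6² = 9. Against an SD of 8 to 12, e runs from 2.25/144 = 1.6% to 9/64 = 14%. Power is then 0.800 to 0.750, and the standard error grows by a factor √((0.75 + e)/0.75), about 1% to 9%.

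**The case against.** The rule is an aim for assessments in general. It suits the BFI, which asks about now and the last 24 hours (section 4.4.4). Nothing says that the primary endpoint must exclude infusion fatigue: the hypothesis is that fatigue rises during chemotherapy and the diet attenuates the rise. A daily fatigue diary is collected expressly to describe variation over a cycle. This is a feasibility pilot whose first aim is adherence and completion.

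Most of this is fair, and it limits the point. The sponsor could legitimately want within-cycle fatigue in the endpoint, but the plan would then have to say so, and section 8.2.7 gives the opposite reason for the gap. The diary is exploratory and does not change the FACIT-F score or its model.

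A reader might infer that the arms are biased, because unblinded staff can choose dates within a wide window. The documents do not support that. The timing rules are the same in both arms, randomisation is stratified by regimen frequency, and nothing indicates that dates would differ by arm. A reader might also infer that the 80% power is wrong; it reproduces on its own inputs. Nor does the rule leave every patient exposed: at nominal week 4 the schedule itself keeps the infusion out for every-2-week and every-4-week patients.

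**Conclusion.** The concern stands as a mismatch between the spacing aim and the recall period of the primary fatigue instrument. A FACIT-F done 3 to 6 days after an infusion always includes it. At nominal week 4 this applies to all compliant days for weekly and every-3-week regimens and to none for the other two. Every-3-week patients also change cycle position between week 4 and week 8, so an apparent recovery in that group could be partly timing.

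The likely consequence is added variance in the 4-week score, and trajectory and SD estimates that carry cycle position into the next trial's planning. How much depends on the regimen mix and the depth of the post-infusion dip, neither of which the documents give. The illustrative fall in power from 0.806 to between 0.800 and 0.750 rests wholly on the assumed dip, proportion and SD. It would be smaller if the planning SD already contains this variation. The day counts rest on infusions falling on the first day of the Table 3 week.

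**What to change.** In section 8.2.7, reconcile the spacing aim with the 7-day recall, or state that the 4-week FACIT-F is meant to include within-cycle fatigue. If the former:

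- **Every-2-, 3- and 4-week regimens.** Complete FACIT-F as late in the cycle as the week 3-5 and 7-9 windows allow, at least 7 days after the last infusion (8 if the recall is read as the seven days before completion) and before the next. Table 4 allows home completion, so the form need not wait for the blood draw.
- **Every-3-week patients, 4-week visit.** Use week 5 (days 28-34, 7-13 days after infusion 2 on day 21), not days 14-20, which would measure the outcome after only 2 to 3 weeks of diet. Week 8 itself also gives 7-13 days, so using it would match the two visits.
- **Weekly regimens.** State that they cannot clear the recall window.
- **Dose delays.** Say how the rule works with the section 17.1 provision that keeps assessments on their planned dates.
- **Data and models.** Record the last infusion date at each FACIT-F. Include the randomisation stratum in the ANCOVA and the mixed model. Prespecify days since last infusion as a sensitivity covariate only, because it is measured after randomisation.

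The cost is protocol wording, one date field and two model terms. There are two downsides. Every-3-week patients may complete the 4-week form up to a week after food provision ends; by day 34 the recall (days 28-34) lies wholly in the self-prepared phase. And 7 days does not fully clear a peak several days after infusion: about 12 days would be needed if the peak is at days 3-5, which is why the wording should ask for late in the cycle and not only for the minimum.

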### 8.2.8 Data collection tables

A Clinical Record form will be completed by the study team using the medical record. **Table 4** lists study-related activities that the participants will experience (weeks 0-8).

Assessment	Study Goal	Assessment Location	Baseline (approx. during week 0)	Week 4	Week 8
On-study data/participant form	Demographics and clinical characteristics	Clinic or home	✓		
3-Day Food Record	Normal dietary habits	Home	✓	✓	✓
ACLS	Physical activity habits	Clinic or home	✓	✓	✓
Functional Assessment of Chronic Illness-Fatigue (FACIT-F)	Aim 1 (patient-reported fatigue)	Clinic or home	✓	✓	✓
14-item Mediterranean Diet assessment tool	Aim 2 (adherence)	Clinic or home	✓	✓	✓
Symptom inventory	Exploratory	Clinic or home	✓	✓	✓
Brief Fatigue Inventory (BFI)	Exploratory	Clinic or home	✓	✓	✓
Brief Pain Inventory (BPI)	Exploratory	Clinic or home	✓	✓	✓
FACT-Cog	Exploratory	Clinic or home	✓	✓	✓
Insomnia Severity Index (ISI)	Exploratory	Clinic or home	✓	✓	✓
Daily diary	Exploratory	Home	Daily for weeks 1-8		
Blood draw	Aim 3 (biomarkers of metabolism and fatigue)	Clinic	✓	✓	✓

**Table 4.** Study-related assessments.

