### **4. Study design**

#### *4.1 Brief description and specific aims*

This will be a feasibility pilot randomized controlled trial performed at a single site. We will recruit 42 patients with cancer who are beginning a chemotherapy regimen and randomize them 2:1 to the intervention group or usual care (28 in the intervention arm and 14 in the usual care arm). The uneven allocation serves to improve recruitment, as some patients are disappointed to be assigned to the usual care arm, and allows us to get more information about the intervention. This will be an open label study (due to the nature of the intervention it is not possible to blind participants, and due to the active involvement of the PI in data acquisition, it is not feasible to blind the PI). At baseline, participants will complete an on-study form that includes demographics and clinical characteristics. They will complete a 3-day food record (ideally from two weekdays and one weekend day), a fasted blood draw, and several questionnaires [i.e., 14-Item Mediterranean Diet Assessment Tool, Functional Assessment of Chronic Illness Therapy – Fatigue (FACIT-F), Aerobics Center Longitudinal Study (ACLS) physical activity questionnaire, Brief Fatigue Inventory (BFI), 27-item Symptom Inventory, Functional Assessment of Cancer Therapy-Cognition (FACT-Cog), Brief Pain Inventory (BPI), Insomnia Severity Index (ISI)]. For the duration of the study, all participants will complete a daily diary that includes their average fatigue level that day. For 4 weeks, we will provide participants in the intervention group with food based on the Mediterranean Diet. We intend this food to be substituted or supplemented with other food of the patients' choosing, though we encourage participants to comply with the Mediterranean Diet for all meals and snacks. During this time we will also provide education regarding the principles and composition of the Mediterranean Diet and how to effectively implement it at home. This education will include materials that encourage behavior change to inspire motivation and adherence to the diet. At 4 weeks, participants will undergo a mid-point evaluation where they will complete the same assessments as at baseline except for the on-study form. For weeks 5-8, participants in the intervention group will be encouraged to follow the Mediterranean Diet though we will not provide food. During the 8-week intervention, we will be in contact with participants in both groups to monitor adverse events and discuss any barriers to consuming the diet (in the intervention group). At 8 weeks, participants will repeat the assessments and undergo an exit interview, which will last approximately 15-30 min. Participants will receive \$20 total to complete baseline and post-intervention measures and those in the intervention group will receive free meals for 4 weeks. Those in the usual care group will be offered the intervention materials and one week of meals *gratis* at the conclusion of the study.

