#### 4.4.4 Exploratory aims and other symptoms and clinical factors

In order to assess the variation in fatigue over the course of a chemotherapy cycle, we will assess average fatigue at the end of each day using a single-item question on a daily diary.

To obtain more precise estimates on the effects of the Mediterranean Diet on cancer-related fatigue and metabolism we will account for several behavioral and clinical factors. For example, several patient-reported outcomes tend to be associated with fatigue (e.g., depression) and we will adjust for these potential factors in our analyses.

1. Aerobics Center Longitudinal Study (ACLS) physical activity questionnaire: The ACLS captures current physical activity and exercise, including walking, climbing stairs, and weight training. We will use this questionnaire to estimate the energy that each participant expends per week on physical activity.
2. Symptom Inventory (SI): The symptom inventory (modified from the MD Anderson Symptom Inventory) includes 19 items that are common in the cancer experience (e.g., pain, distress, lack of appetite, numbness and tingling, fatigue), as well as 8 items related to how much these symptoms interfere with activities of daily living and quality of life. As many symptoms often correlate with each other including fatigue (i.e., symptom clustering), it is important to capture the change in many symptoms from baseline to post-intervention. Exploratory analyses will probe whether adherence to the diet or high consumption of any dietary component correlates with the change in any of these symptoms over time.
3. Brief Fatigue Inventory (BFI): The BFI is a 10-item fatigue questionnaire that is also validated and commonly used. It captures fatigue *now* as well as the usual and worst in the last 24 h. It also includes 6 single-item questions regarding how fatigue has interfered with general activity, mood, work, etc.
4. FACT-Cog: The FACT-Cog is a 41-item questionnaire designed to assess cognitive challenges identified by patients with cancer.
5. Brief Pain Inventory: The Brief Pain Inventory (BPI)-Short Form is a 15-item questionnaire designed to assess the severity of pain and its impact on functioning.

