6. Insomnia Severity Index (ISI): The Insomnia Severity Index (ISI) is a brief 7-item questionnaire that was designed to assess the severity of both nighttime and daytime components of insomnia.

Some study data (e.g., questionnaires) will be collected electronically using REDCap software. REDCap is a secure, web-based application for building and managing online surveys and databases and is made available through the CTSI. REDCap will be used to send a secured web link to each study subject, and a built-in scheduling function will allow for re-contact at a pre-specified time to remind subjects to complete the questionnaires if needed. All data forms will be checked immediately by the REDCap system as they are being completed by the study subject to ensure completeness (i.e., that no question was skipped unintentionally), and a pop-up message feature will be used to encourage a response. For participants who prefer paper-based questionnaires, a paper version will be provided for them to complete and return to the study staff in person or in a postage-paid envelope. In this case, a study staff member will enter the responses into the REDCap database.

There are a total of 11 questionnaires and survey assessments that will be completed. The on-study form will be completed at baseline only; the daily diary will be completed every day; the others will be completed at baseline, 4 weeks, and 8 weeks.

- On study (demographics and clinical characteristics; baseline only)
- FACIT-F (fatigue)

- Daily diary (single-item fatigue question)
- 14-item Mediterranean Diet assessment
- 3-day food record
- ACLS (activity)
- Symptom inventory
- BFI (fatigue)
- FACT-Cog (cognition)
- BPI (pain)
- ISI (sleep)

The daily diary will take about 10 seconds each day and the other questionnaires should take approximately 30-45 minutes total to complete.

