#### *8.2.5 Randomization procedures*

Randomization will be revealed to the participant at the end of the baseline assessments, before delivering the instructional portion of the intervention.

We will employ two treatment arms in a 2:1 allocation ratio:

1. Mediterranean Diet: an 8-week intervention entailing education of the Mediterranean Diet and delivery of Mediterranean Diet-inspired meals for 4 weeks.
2. Usual care: completion of assessments, with no intervention and usual care for their cancer.

Consented subjects will be randomized with a computer-generated random numbers table with block sizes of 3 and 6 and stratified based on how frequently they will be receiving chemotherapy (weekly, biweekly, or every 4 weeks vs. other). The random numbers tables will be generated centrally by [name], the project biostatistician, or a designee. A total enrollment of 42 subjects is planned.

Participants cannot be blinded due to the nature of the intervention. PI blinding is also not feasible given that the PI will play an active role in recruitment, intervention delivery, data acquisition, and analysis.

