#### *17.4.2 Aim 2: Patient-reported fatigue*

To provide estimates of efficacy comparing the Mediterranean Diet to usual care for alleviating fatigue, we will evaluate between-arm difference in mean change in FACIT-F fatigue subscale score from baseline to 4 weeks in an ANCOVA model. The outcome will be FACIT-F fatigue score at 4 weeks with arm included as a fixed effect and FACIT-F fatigue score at baseline as a covariate. To assess the moderating effect of the baseline level of fatigue we will test arm×baseline interaction. To further evaluate the longitudinal trajectory of fatigue and the maintaining effect of the intervention, we will incorporate FACIT-F fatigue score measured at all time points (T1, T2, T3) in a repeated measures linear mixed model. The impact of patient's variables (e.g., age, gender, body mass index) on the results will be assessed by adding the covariates to the models. The results of the analyses together with the estimates of distribution parameters (e.g., mean, SD) of T1-T3 FACIT-F fatigue score values as well as the change scores will be used in planning a future randomized trial.

We expect all measures of cancer-related fatigue to increase over the course of chemotherapy, though we hypothesize that the differences will be attenuated in the intervention group. We will also compare our baseline-to-post-intervention change scores to those obtained via historical controls (e.g., [name] et al., 2018).

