#### *17.4.4 Exploratory analyses*

In an exploratory analysis, we will correlate Mediterranean Diet score with patient-reported fatigue using the FACIT-F fatigue score at 4 weeks and 8 weeks. We expect that the majority of participants will improve their Mediterranean Diet score, and that 4 and 8 week scores will range from 5-14 in the intervention group (higher is better). We expect that the fatigue subscale of the FACIT-F will range from 0-43 out of 52 based on a historical dataset (Kleckner et al.; a higher score indicates less) and that FACIT-F total scores will range from 44-160 out of 160^161 (higher is better well-being). We will also assess correlations between baseline Mediterranean Diet score (proxy for improvement in diet quality) and change in fatigue to evaluate the influence on baseline diet on the development of fatigue. Further, we will assess the change in the Mediterranean Diet score and the change in fatigue to see if a greater shift in diet led to a greater prevention of fatigue.

Other measures collected via patient-reported outcome questionnaires (e.g., BFI, Fact-Cog) will be analyzed using similar methodology as outlined in the Aim 2 (FACIT-F score analysis).

**Because of the small sample size in this study and the resulting low statistical power, these secondary and exploratory analyses will be interpreted very cautiously and only used to aid in the designing of a study for our larger trial and generation of new hypotheses.**

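### The daily fatigue diary starts only after allocation is revealed, so it has no baseline of its own; a diary run-in in week 0 would supply one cheaply

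*Combined protocol and SAP*

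**What the plan says.** - **Schedule.** Table 4 (8.2.8) lists the diary as "Daily for weeks 1-8" and shows no entry for it in the week-0 baseline column. Section 4.4.4 separates it from the other instruments: "the daily diary will be completed every day; the others will be completed at baseline, 4 weeks, and 8 weeks". Section 4.1 says "For the duration of the study, all participants will complete a daily diary". That could be read as including the baseline week, but 8.2.6 counts the 8 study weeks after the baseline week, and Table 4 is explicit.
- **Allocation.** Section 8.2.5: "Randomization will be revealed to the participant at the end of the baseline assessments, before delivering the instructional portion of the intervention". Every scheduled diary day is therefore post-allocation.
- **Purpose.** Section 4.4.4 introduces the diary with "In order to assess the variation in fatigue over the course of a chemotherapy cycle". It also counts the diary among its 11 questionnaires and survey assessments.
- **Analysis.** Section 17.4.4 says that other patient-reported questionnaire measures, with BFI and FACT-Cog as examples, "will be analyzed using similar methodology as outlined in the Aim 2". The Aim 2 model in 17.4.2 is an ANCOVA of the 4-week score with "FACIT-F fatigue score at baseline as a covariate", followed by a mixed model over the three time points. Section 17.4 does not name the diary or give it a summary measure, model or contrast.
- **Opportunity.** Section 8.2.6: "participants will have approximately 1 week to complete at-home baseline assessments".

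**The concern.** The plan's general approach to a patient-reported outcome is to adjust for the same instrument's value before treatment. The diary is the only repeated patient-reported measure without one. Neither an own-baseline ANCOVA nor a diary change score can be computed for it.

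Two things are at stake. The first is precision: an arm comparison among about 22 and 11 people gains from a good baseline covariate. The second is interpretation. The trial's hypothesis is that the diet prevents a rise in fatigue, and a diary that begins in week 1 has no starting level from which to measure a rise.

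The diary is worth some care here. Section 2.1.1 says that fatigue peaks several days after each infusion. Section 17.1 says that the 4- and 8-week visits fall at the end of a cycle in one stratum and mid-cycle in the other. The diary is the measure that runs through whole cycles. A baseline week that is not collected cannot be recovered later.

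**Working it through.** **Inputs.** From 17.1: 33 evaluable participants (22:11), two-sided alpha 0.15, effect size 0.75 SD, and a baseline to 4-week correlation of 0.50 for FACIT-F. The documents give no correlation, SD or effect size for the diary. Applying the FACIT-F values to it is an assumption made for illustration.

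**Step 1: reproduce the plan's figure.** ANCOVA leaves a residual SD of √(1 − ρ²) = √(1 − 0.25) = 0.866. The standard error factor is √(1/11 + 1/22) = 0.369. Then 0.75 / (0.866 × 0.369) = 2.345. Subtracting the critical value 1.440 leaves 0.906, which is 81.7% power (80.7% with the noncentral t on 30 df). The stated 80% reproduces, and it relies on the baseline covariate.

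**Step 2: drop the covariate.** With SD 1, 0.75 / 0.369 = 2.031. Subtracting 1.440 leaves 0.591, which is 72.3% power (t: 71.2%). The effect detectable with 80% power rises from 0.73 to 0.84 SD. The evaluable number needed for 80% power rises from 33 to 42.

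**Step 3: vary the assumed diary correlation.** The variance cut from own-baseline adjustment, against no adjustment, is ρ².

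| Assumed ρ | Residual variance 1 − ρ² | Variance cut |
|---|---|---|
| 0.3 | 0.91 | 9% |
| 0.5 | 0.75 | 25% |
| 0.7 | 0.51 | 51% |

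**Step 4: use the fairer comparator.** FACIT-F, BFI and the symptom inventory, which has a fatigue item, are all collected at baseline, so one of them could stand in as covariate. Assume that such a proxy correlates 0.3 to 0.4 with the diary outcome. Power is then 75.5% to 78.1% (t: 74.3% to 77.0%), between the no-covariate and own-baseline figures. The gain from an own baseline at 0.5 over the proxy, in equivalent evaluable participants, is:

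- proxy at 0.4: 33 × 0.84 / 0.75 = 37
- proxy at 0.3: 33 × 0.91 / 0.75 = 40

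In power terms the gain is about 4 to 6 points (81.7 − 78.1 = 3.6; 81.7 − 75.5 = 6.2).

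**Limit of the calculation.** Averaging many diary days changes the outcome's variance, so these figures compare covariate choices for one outcome. They do not forecast the diary's power.

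**The case against.** The strongest reply is that the plan promises no arm comparison of the diary. Its stated purpose is variation within a cycle, which needs no pre-allocation value. Section 17.4.4 does not name it and asks only for similar methods. This stands: a reader might infer that the SAP prescribes a model that it cannot fit, but that rests only on the diary being counted among the 11 questionnaires. If 17.4.4 does not cover the diary, however, then up to 56 daily scores per person have no defined analysis, which also needs a sentence.

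A reader might also infer that only an unadjusted comparison is possible. The documents do not support that. Baseline FACIT-F, BFI or the symptom-inventory fatigue item could serve as covariate, and the BFI asks about usual fatigue in the last 24 hours, close to what the diary asks. Section 17.4.2 already allows added covariates. A proxy recovers part of the loss, although none is named for the diary.

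The value of a baseline week is itself uncertain. Section 8.2.7 prefers baseline before the first infusion but permits it later, so the week would precede chemotherapy for some and fall mid-cycle for others. Its correlation with on-treatment fatigue could be below 0.5.

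Finally, a 28-day mean alone would discard the within-cycle pattern that the diary was included to describe, and it covers different numbers of cycles by regimen. Both points stand and shape the fix.

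**Conclusion.** The point holds as a low-cost improvement to an exploratory measure. The diary has no pre-allocation value, so its own-baseline ANCOVA and any change from the starting level are unavailable, and this cannot be repaired afterwards.

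The size rests on assumed correlations: a variance cut of 9% to 51% against no adjustment for ρ from 0.3 to 0.7, or about 33 becoming 37 to 40 evaluable participants against a proxy covariate at 0.3 to 0.4 when the own baseline correlates 0.5.

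Two stronger conclusions are tempting. One is that the missing baseline costs the equivalent of 33 becoming 44 to 65 participants (33 / 0.75 and 33 / 0.51). That compares only with no adjustment and takes only correlations of 0.5 to 0.7, which the documents do not support for the diary. The other is that chance imbalance would bias the comparison. Randomisation keeps an unadjusted comparison unbiased, so the cost is in precision. The primary FACIT-F analysis, the sample size and the feasibility criteria are untouched, and 17.4.4 already says that exploratory results will be read cautiously.

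**What to change.** 1. **Table 4 and 4.4.4:** start the diary at consent, in the week-0 baseline period, with these entries made before allocation is revealed. Align the wording in 4.1.
2. **17.4.4:** name the diary. Compare arms on mean diary fatigue over weeks 1-4, and separately over weeks 5-8, by ANCOVA with the mean pre-allocation diary score as covariate.
3. **Same section:** adjust for the chemotherapy-frequency stratum. A 28-day window holds 4, 2 or 1 whole cycles for weekly, every-2-week and every-4-week regimens, but 28/21 = 1⅓ cycles for every-3-week regimens. Stratum adjustment separates the whole-cycle regimens from the rest. It does not equalise the number of infusions within the first stratum.
4. **Same section:** keep the description of within-cycle variation as a separate analysis.

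The cost is one more diary page, a few sentences of SAP text, and about 7 × 10 = 70 seconds per participant, using the diary time given in 4.4.4. Some participants will have fewer baseline days when the baseline period is compressed, and the baseline week will not mean the same thing for everyone. A side benefit is that the pilot would estimate the diary's own baseline to follow-up correlation, which a larger trial using the diary would need.
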